### Primary objectives

- To describe the demographics and clinical characteristics of patients who have received palbociclib combination with aromatase inhibitor (as prescribed by the Physician) in menopausal state as initial endocrine therapy in MBC or with fulvestrant after progression on prior endocrine therapy.
- To summarize adjuvant therapies received for the treatment of early or locally advanced breast cancer (Stages 0-IIIa).
- To describe treatments received in the advanced/metastatic setting, before and after palbociclib combination use.
- To describe dosing and dose changes, interruptions, delays, and discontinuations associated with palbociclib use in clinical practice.
- To describe supportive therapies received by patients while receiving palbociclib combination treatments.
- To determine in overall population and defined subgroups, clinical outcomes including (but not limited to):
  - Proportion of patients who are progression free at specific intervals (eg, 6, 12, 18 months).
  - Objective response rate (ORR) - depending on availability of follow-up data.
  - Proportion of alive patients 1 and 2 years post palbociclib combination initiation - depending on availability of follow-up data (sample size permitting).

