## 9. RESEARCH METHODS

### 9.1 Study Design

This is a post marketing, retrospective, non-interventional study (NIS). The study will be conducted as a retrospective medical record review of patients who have received palbociclib combination with aromatase inhibitor (as prescribed by the Physician) in menopausal state as initial endocrine therapy in MBC or with fulvestrant after progression on prior endocrine therapy. It will comprise of an initial screening and eligibility assessment of patients followed by data collection from eligible patient records.

Data collection will be conducted using a predesigned electronic case report form (eCRF). Eligible physicians will be invited to complete the eCRF of patients that meet the study criteria. Each eCRF will take around 25 minutes to complete. Patient eligibility will be confirmed by treating physicians. In order to allow for a sufficiently long observational window, treating physicians will be asked to go back to a specific point in time, the index date, and sequentially select the medical records of the next 'n' patients who meet the inclusion criteria. The 'index date' will be defined as 60 days after the physician first prescribed palbociclib + partner therapy following the availability of specific indication in the market (eg, if palbociclib + aromatase inhibitor was available on 25 October 2016 in India and the physician initiated a patient on palbociclib with aromatase inhibitor the next day, the index date will be 26 December 2016). The index date will differ for the specific indications/combination partners if approved on different dates.

The proportion of patients treated in accordance with the first line versus second or later line setting for metastatic disease will be approximately 7:3, as has been observed in the real world practice.

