#### Patient inclusion criteria

Patients must meet all of the following inclusion criteria to be eligible for inclusion in the study:

- $\geq 18$  years old females.
- HR+/HER2- breast cancer diagnosis with confirmed metastatic or advanced disease.
- Received palbociclib with aromatase inhibitor (as prescribed by the Physician) as initial endocrine therapy in postmenopausal MBC patients or with fulvestrant in patients who have progressed on prior endocrine therapy

- Patients on LHRH agonists for ovarian function suppression in pre- or perimenopausal stage only if prescribed palbociclib with fulvestrant.
- No prior or current enrolment in an interventional clinical trial for ABC/MBC.
- Minimum of 3 months of follow up data since palbociclib with fulvestrant initiation, or minimum of 6 months of follow up data since palbociclib with aromatase inhibitor initiation.

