### 9.3 Variables

**Table 1. List of Study Variables**

Variable	Role	Data Source(s)	Operational Definition
Patient demographics	Baseline Sub-group identifier	Patient records	Age, ethnicity, weight, height, biomarker status, family history of breast cancer.
Clinical characteristics	Baseline Sub-group identifier	Patient records	Time since diagnosis, staging, node status, menopause status. ECOG/Karnofsky functional status, diagnosis for which palbociclib combination was prescribed, sites of metastases, de novo vs. recurrent disease.
Comorbid conditions	Baseline Sub-group identifier	Patient records	Comorbid conditions.
Early treatment history	Baseline Sub-group identifier	Patient records	Adjuvant treatments received since breast cancer diagnosis, time since end of adjuvant treatment, surgery/radiotherapy received.
Advanced treatment history	Baseline Sub-group identifier	Patient records	Treatments and supportive therapies received since metastatic/advanced HR+/HER2- diagnosis, duration of treatments, reasons for regimen changes.
Palbociclib combination treatment	Exposure Sub-group identifier	Patient records	Starting dose, duration of treatment, line of treatment, changes in dose, interruptions, cycle delays and discontinuations; where possible reasons for change in treatment.
Clinical outcomes	Outcomes	Patient records	Proportion progression free, ORR, TTP, PFS, patient death, 1-year and 2-year survival in all patients and within specific subgroups.

PFIZER CONFIDENTIAL

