5 ENDPOINTS AND COVARIATES**5.1 EFFICACY/EFFECTIVENESS ENDPOINT(S)**

- Treatment success of the patients treated with palbociclib with aromatase inhibitor (as prescribed by the Physician) will be progression free i.e. complete response, partial response or stable disease at the end of regimen.

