For all the patients' line of treatment for Palbociclib combination started will be given in frequency and percentage, time (months) from diagnosis of breast cancer to start of Palbociclib combination will be presented as mean, median, standard deviation and range value (minimum and maximum). **CCI**

CCI

[figure not shown]
- **Clinical Outcome**

For all the patients initially recorded responses like complete positive response to the disease, partial positive response to the disease, stable disease and progressive disease, will be summarized with frequency counts (n) and percentages (%). Moreover, based on initial response, objective response rate (ORR) and clinical benefit rate (CBR) will be calculated and presented as percentage.

CCI

PFIZER CONFIDENTIAL

PFIZER CONFIDENTIAL

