Yes	n (%)	xx (xx.x)
Stable disease		
Yes	n (%)	xx (xx.x)
Progressive disease		
Yes	n (%)	xx (xx.x)
Objective Response Rate (ORR)		
Yes	n (%)	xx (xx.x)
Clinical Benefit Rate (CBR)		
Yes	n (%)	xx (xx.x)

CCI

Abbreviations: N = number of subjects in Palbociclib group; n = number of subjects in specified category

[figure not shown]
Note 1: Percentages are based on the number of subjects in the Palbociclib group.

PFIZER CONFIDENTIAL

Table 11.1 Clinical Outcome by line of treatment (first line vs. second and later line)

A large black rectangular redaction box covers the majority of the page content below the table caption. Within this redaction, the letters 'CCI' are printed in large, bold, red font, likely representing the first few letters of the table title.

CCI

A horizontal black redaction bar is located at the bottom of the page, obscuring the bottom portion of the page content.

PFIZER CONFIDENTIAL

PFIZER CONFIDENTIAL

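### On the visible text, SAP 7.2 takes ORR and CBR from the initial response, so a response reached after initial stable disease is not counted in ORR

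*SAP*

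**What the plan says.** The protocol lists ORR among the clinical outcomes of its primary objectives (section 8): "Objective response rate (ORR) - depending on availability of follow-up data". Table 1 in section 9.3 lists it again without further definition: "Proportion progression free, ORR, TTP, PFS, patient death, 1-year and 2-year survival in all patients and within specific subgroups". Neither place says which assessment counts, nor whether best response is meant.

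The SAP supplies the rule. The Clinical Outcome paragraph of 7.2 begins "For all the patients initially recorded responses like complete positive response to the disease", continues through partial response, stable disease and progressive disease, and then states "based on initial response, objective response rate (ORR) and clinical benefit rate (CBR) will be calculated and presented as percentage". The visible text does not define *initial response*. Table 11 in Appendix 1 has rows for the same four categories, then ORR and CBR, in the same order. Its rows carry no time point, and its note bases percentages on all subjects in the palbociclib group. Table 11.1 repeats the table by line of treatment.

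SAP 5.1 defines a different quantity, treatment success, as "complete response, partial response or stable disease at the end of regimen".

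Redacted blocks follow the sentence in 7.2, sit inside Table 11, and also appear in Protocol 9.7 (Data Analysis).

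**The concern.** A reader who meets an ORR row without qualification is likely to take it as the share of patients who ever responded on treatment. A rule that stops at the first recorded response answers a narrower question. It leaves later responses unused, although eligibility demands follow-up: "Minimum of 3 months of follow up data since palbociclib with fulvestrant initiation", and at least 6 months with an aromatase inhibitor.

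The study is descriptive, so the percentage is itself the result. The protocol's rationale says such data should help inform treatment decisions. If the row is read as best response, the figure for a primary-objective outcome may be too low, and nothing visible in Table 11 warns the reader.

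**Working it through.** The plan states no expected ORR, so there is no figure of its own to reproduce. The check has three parts.

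**1. Direction.** Take one denominator N for both versions, as the Table 11 note implies. The order below is within the period before progression or next therapy.

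| First recorded response | Later recorded response | ORR on first response | ORR on best response |
|---|---|---|---|
| CR or PR | any | counted | counted |
| SD | PR or CR | not counted | counted |
| SD | no PR or CR | not counted | not counted |
| PD | (period ended) | not counted | not counted |

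First-response responders are a subset of best-response responders, so ORR(first) ≤ ORR(best). Only the second row separates them.

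CBR behaves differently. The visible text does not list its components. If it counts any stable disease as benefit, a move from SD to PR leaves it unchanged. The time point still needs stating, because the same sentence governs both rates.

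**2. Points per missed responder.** Inputs: about 150 patients (Protocol 9.5), and the protocol's planned split, "first line versus second or later line setting for metastatic disease will be approximately 7:3" (9.1). This gives 150 × 7/10 = 105 first-line and 150 × 3/10 = 45 later-line patients. For 10 later responders not counted, the loss is 10/N:

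- all patients: 10/150 = 6.7 points
- if all 10 are first line: 10/105 = 9.5 points
- if all 10 are second or later line: 10/45 = 22.2 points

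The last two are scale factors for Table 11.1, not forecasts. Each needs all ten to fall in one stratum.

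**3. Illustration of the total.** Shortfall = (share with SD first) × (share of those who later reach PR or CR). The documents give neither share; both are assumed here.

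| Later response among SD-first patients | SD first 40% | SD first 60% |
|---|---|---|
| 0% | 0 points (0 of 150) | 0 points (0 of 150) |
| 10% | 4 points (6) | 6 points (9) |
| 20% | 8 points (12) | 12 points (18) |
| 30% | 12 points (18) | 18 points (27) |

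The documents support the direction. They do not support any particular cell.

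**The case against.** The strongest reply is that an undercount is not proven. *Initial response* is undefined, and the eCRF on which the SAP is based (version 0.09, per SAP 2) is not visible. The phrase could mean the first of several responses, or simply the one response field on the form. The redacted blocks in SAP 7.2, Table 11 and Protocol 9.7 are where a later-response rule might sit. All of this stands, and it limits the point to the visible text. It does not remove it: if a later-response rule exists, the visible sentence has to be reconciled with it, and if *initial* means something else, the SAP must say so.

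It can also be said that a first-response rate is legitimate in a descriptive chart review, because best response depends on how long and how often each patient was assessed. That is fair. A clearly labelled first-response rate would be defensible; an unlabelled one called ORR is the difficulty.

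A reader might infer two stronger points that the documents do not support:

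- **That SAP 5.1 and 7.2 contradict each other.** They define different measures. A patient with SD first and PR at the end is a success under 5.1 and a non-responder under 7.2, but so is a patient with SD throughout, because 5.1 counts SD. That example does not isolate timing. A patient with PR first and progression at the end shows only that response and final status can differ.
- **That one cannot tell what fills Table 11.** Its visible rows follow the 7.2 paragraph in the same order, so on the visible text they hold initial response. What is missing is the label.

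**Conclusion.** The point holds in a limited form. On the visible text and the natural reading of *initial response*, SAP 7.2 counts a patient with initial SD and later PR or CR as a non-responder. With a common denominator, ORR so defined can only equal or fall below ORR on best recorded response. The amount cannot be derived from the documents and may be zero; the 0 to 18 points above rest entirely on assumed shares. It would be wrong to conclude that the reported ORR will be materially too low, or that no later-response rule exists anywhere in the plan. The point is worth correcting because ORR falls under a primary objective, any error runs in one direction, and the correction is small. Confidence is medium, given the undefined term, the unseen eCRF and the redactions.

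**What to change.** - **SAP 7.2:** define ORR as best recorded response (CR or PR) from palbociclib start to progression, next therapy or data collection, whichever is first. State CBR on the same best-response basis and list its components.
- **Tables 11 and 11.1:** label the ORR and CBR rows 'best recorded response'. Keep the initial response as a separate row, 'response at first recorded assessment', and report follow-up time beside it.
- **SAP 5.1:** give end-of-regimen success its own labelled row. Its definition need not change for this point.
- **Redacted text:** if it already contains a later-response rule, bring the visible sentence into line with it.
- **Fallback:** if the eCRF holds only one response per patient, label the ORR and CBR rows 'at first recorded assessment' and state that ORR may understate best response.

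The cost is a few sentences and row labels in a SAP that, by its section 7.1, is to be final before database lock. The visible protocol gives ORR no time point, so no visible protocol definition changes. If the eCRF already records later responses, no new data are needed. If not, collecting them could mean reopening about 150 charts, which the fallback avoids.

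The downside is that best response depends on follow-up length, with minimums of 3 months for fulvestrant and 6 for aromatase inhibitor, and on assessment frequency in routine care. The report should say so.

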**Table 2. Sample Size for Medical Record Review**

City	Approximate Number of Physicians	Number of Patient Records
Mumbai	1	20
Pune	1	10
Delhi	2	40
Bangalore	2	20
Kolkata	1	10
Vellore	1	10
Jaipur	1	20
Chennai	1	20
Total (approximate):	10	150

The sample size above (city, physician number per city, number of patient records and total samples) should be considered flexible, with scope to increase based on availability of medical records with each participating physician/site.

The objectives do not state any hypotheses and therefore, do not require any statistical testing. All the analyses will be descriptive and so sample size calculations are not required.

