## **9.7 Data Analysis**

Detailed methodology for summary and statistical analyses of data collected in this study will be documented in a statistical analysis plan (SAP), which will be dated, filed and maintained by the sponsor. The SAP may modify the plans outlined in the protocol; any major modifications of primary endpoint definitions or their analyses would be reflected in a protocol amendment.

All analyses are to be descriptive and so all methods to be used will reflect this descriptive nature. The specific method that will be used depends on type of variable being analyzed and those methods are:

- Categorical variables – will be described using:
  - Number of observations (n);
  - Number and percent (%) within each category;
  - Number of missing observations.
- Numeric variables – will be described using:
  - Number of observations (n);
  - Mean & Standard deviation;
  - Minimum, Maximum, Median and 1st & 3rd Quartiles;
  - Number of missing observations.

PFIZER CONFIDENTIAL

- Time to event – will be described using:
  - A Kaplan-Meier chart that will visually estimate the distribution of times to some events, eg, progression, and will consider those patients for which the event has not yet occurred;
  - 1-year and 2-year rates, median or some more appropriate percentiles if the median time is not reached in the sample.

Missing data will be excluded on a case by case basis and will not be imputed. This will mean that each table will not necessarily be based on the same number of patients.

All statistical analyses will be conducted with general purpose statistical software (SAS) version 9.0 or higher

PFIZER CONFIDENTIAL

Palbociclib

A5481145, PD-0332991 NON-INTERVENTIONAL STUDY PROTOCOL

Final Protocol version 1.0, 19-Oct-2020

CCI

PFIZER CONFIDENTIAL

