7 STATISTICAL METHODOLOGY AND STATISTICAL ANALYSES**7.1 STATISTICAL METHODS**

Analysis of the data will be performed by the Biostatistics and Statistical Programming team. All statistical analyses will be performed using STATA 13.0 Version or higher. The SAP will be finalized before database lock.

The following standard descriptive summaries will be presented:

[figure not shown]
[figure not shown]
Descriptive statistics for continuous data:

The continuous data will be summarized using the number of observations (n), arithmetic mean (mean), standard deviation (SD), median, minimum value (min), and maximum value (max).

The number of observations (n) will be presented with no decimal place, mean and median will be presented up to one decimal place from the original value, SD up to two decimal places from the original value and (min, max) as an original value.

Descriptive statistics for categorical data:

PFIZER CONFIDENTIAL

The categorical variables will be summarized using the frequency count (n) and percentage (%) for each possible value. The frequencies will be presented up to 0 decimal places, percentage up to 1 decimal place.

All the analysed variable will be presented by the line of treatment (1st line of treatment and 2nd and later line). If data are not available, a missing category will be presented. Statistical tests, if any, will be performed at 5% level of significance. The denominator for percentages will be based on the number of patients appropriate for the purpose of the analysis.

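### ORR and CBR are planned as n (%) with no confidence interval, while the SAP leaves room for unspecified 5% tests that do not fit its descriptive design

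*SAP*

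**What the plan says.** **Outcome reporting.** Under Clinical Outcome, SAP 7.2 tabulates the recorded responses and adds that "objective response rate (ORR) and clinical benefit rate (CBR) will be calculated and presented as percentage". The general rule in SAP 7.1 is the same: "The categorical variables will be summarized using the frequency count (n) and percentage (%) for each possible value". In the Table 11 shell (SAP Appendix 1) the ORR and CBR rows carry n (%) only, with the footnote "Note 1: Percentages are based on the number of subjects in the Palbociclib group". SAP 7.1 also requires all analysed variables to be shown for first line against second and later line. Table 11.1 is the by-line version of Table 11; only its title is visible.

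**Testing.** SAP 7.1 says "Statistical tests, if any, will be performed at 5% level of significance". SAP 3.1 (hypotheses) and 3.2 (decision rules) are both marked not applicable. Protocol 9.5, below Table 2, says "The objectives do not state any hypotheses and therefore, do not require any statistical testing". Protocol 9.7 says "All analyses are to be descriptive and so all methods to be used will reflect this descriptive nature".

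**Status of the outcome.** ORR is listed under the sixth primary objective (Protocol 8, SAP 2.2), to be determined overall and in defined subgroups, subject to available follow-up.

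**The concern.** Two features of the plan work against each other. The outcome estimates get no statement of precision, while the one inferential device the visible SAP mentions is a significance level attached to no hypothesis, variable, comparison, sidedness or multiplicity rule.

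The test sentence closely follows the rule that every variable is split by line of treatment, so by-line p-values are the most natural use of it. The eligible settings differ by design: an aromatase inhibitor combination as initial endocrine therapy, with at least 6 months of follow-up, or a fulvestrant combination after progression, with at least 3 months. Protocol 9.9 itself warns of channeling bias. A p-value between lines would therefore have no clear interpretation.

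Without intervals, a percentage to one decimal place from about 45 patients looks as firm as one from 150. Protocol 7 says the results should help inform treatment decisions, so readers need to see how uncertain they are. No precision target is given elsewhere, because Protocol 9.5 treats a sample size calculation as unnecessary.

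**Working it through.** **Inputs from the documents**
- Protocol Table 2, records: 20 + 10 + 40 + 20 + 10 + 10 + 20 + 20 = 150. Physicians: 1 + 1 + 2 + 2 + 1 + 1 + 1 + 1 = 10. Both stated totals are reproduced.
- Protocol 9.1, first line to later line about 7:3: 150 × 0.7 = 105 and 150 × 0.3 = 45.

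**Assumptions.** The documents give no expected ORR or CBR, so rates from 20% to 80% are used. The 105/45 split treats the approximate ratio as exact.

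**Step 1: simple 95% half-width at 50%, 1.96 × √(0.25/n)**
- n = 150: 8.0 points
- n = 105: 9.6 points
- n = 45: 14.6 points

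**Step 2: exact (Clopper-Pearson) half-widths over 20–80%**

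| n | Half-width (points) | Example |
|---|---|---|
| 150 | 6.7 to 8.3 | 60/150 = 40.0%, 95% CI 32.1 to 48.3 |
| 105 | 8.1 to 9.9 | 42/105 = 40.0%, 95% CI 30.6 to 50.0 |
| 45 | 12.5 to 15.3 | 18/45 = 40.0%, 95% CI 25.7 to 55.7 |

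All three examples would print as 40.0%. Wilson half-widths are about 0.3 to 1.3 points narrower.

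**Step 3: difference between lines.** With 50% in both groups, 1.96 × √(0.25/105 + 0.25/45) = 17.5 points. Over seven assumed rate pairs between 25% and 80%, the half-width is about 16 to 17.5 points.

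**Step 4: possible effect of physician clustering.** If records are shared equally within Delhi and within Bangalore, Table 2 gives five physicians with 20 records and five with 10.
- Weighted cluster size: (5 × 20² + 5 × 10²)/150 = 2500/150 = 16.67.
- Design effect: 1 + 15.67 × ICC. With an assumed within-physician correlation (ICC) of 0.05 or 0.10, it is 1.78 or 2.57.
- Overall half-width at 50%, using t with 10 − 1 = 9 df (2.262): 2.262 × √(0.25/150 × 1.78) = 12.3 points, and 2.262 × √(0.25/150 × 2.57) = 14.8 points.

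**Step 5: the testing sentence against the rest of the plan.** SAP 3.1 and 3.2 leave nothing to test and no rule for deciding. Protocol 9.5 says testing is not required, and Protocol 9.7 calls for descriptive methods. No visible analysis in SAP 7.2 names a test, and no visible shell has a p-value row or column. In the visible text the 5% level serves no stated analysis.

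**The case against.** The strongest reply has five parts.

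- **The SAP follows the protocol.** Protocol 9.7 describes categorical variables by n and %, and neither document promises intervals. This stands: their absence is not a departure from the protocol. It is a weakness of method for an outcome named in a primary objective.
- **Readers can compute an interval themselves.** Table 11 gives the count and N, so for a simple binomial proportion this is true. It does not help a reader who sees only the reported percentage, and the calculation should not be left to each reader.
- **Testing is not forbidden.** A reader might infer that the protocol rules tests out. It does not. It says testing is not required, and Protocol 9.7 lets the SAP depart from the protocol's plans, asking for an amendment only when a primary endpoint or its analysis changes in a major way. The exact charge is inconsistency: the SAP records no such change and states no hypothesis.
- **Tests are permitted, not planned.** A reader might also go on to count by-line comparisons and predict false positives. The documents do not support such a figure. No tests are listed, many baseline variables should truly differ by line, and the response rows in Table 11 all derive from one variable.
- **Redactions.** Blacked-out text follows the ORR and CBR sentence, the Table 11 rows and the Table 11.1 title. A reader might infer that no outcome has an interval. That cannot be known for progression-free or survival proportions, nor can a redacted use of the 5% level be excluded. The ORR and CBR sentence and the Table 11 rows are themselves fully visible and show no interval.

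On clustering, the correlations are assumed, and Protocol 9.5 calls the physician and record numbers flexible. By line, some physicians may contribute few or no later-line patients, so a fixed 9 df would not be justified there.

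**Conclusion.** The point holds for ORR and CBR, and for the testing sentence. As visible, the plan reports two outcome rates without precision, where the 95% half-width at 50% is about 8 points overall and about 15 points in the later-line group. A by-line difference would carry about ±16 to 17.5 points. These figures rest on 150 patients, an exact 7:3 split, assumed rates and independent patients. If patients of the same physician resemble each other (ICC 0.05 to 0.10, Table 2 block sizes), the overall half-width would be about 12 to 15 points with a t reference.

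The 5% sentence is inconsistent with SAP 3.1 and 3.2 and with the protocol's descriptive plan. It is an unexplained permission; the visible text does not show that p-values will be produced. For the other outcomes under objective 6, the documents support only a conditional request. This is worth correcting in the SAP, but it does not undermine the study design.

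**What to change.** 1. **SAP 7.1:** replace the sentence on 5% tests with a statement that no hypothesis tests will be done and that differences between lines of treatment are descriptive. If a redacted analysis does need a test, name the test, variable, comparison and sidedness there, and reconcile it with SAP 3.1 and 3.2.
2. **SAP 7.2 and Tables 11 and 11.1:** add two-sided 95% Clopper-Pearson or Wilson intervals for ORR and CBR, overall and by line. Name the method, and use the same denominator as the percentage.
3. **Progression-free and 1- and 2-year survival proportions:** do the same if the redacted text does not already specify it, with Kaplan-Meier-based intervals where follow-up is censored.
4. **Optional sensitivity analysis:** an interval for the overall ORR and CBR with physician as the cluster, with degrees of freedom set by the number of physicians who actually contribute.

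The cost is a few sentences in the SAP, an extra column or row in two shells, and a few lines of code. No new data or patients are needed. The clustered intervals would probably be wider than the binomial ones.
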